#### **4.4 Early Withdrawal of Subjects**

##### **4.4.1 When and How to Withdraw Subjects**

Subjects who do not complete the study protocol will be considered to have prematurely discontinued the study. The reasons for premature discontinuation (for example, voluntary withdrawal, toxicity, death) must be recorded on the case report form. Final study evaluations will be completed at the time of discontinuation. Potential reasons for premature discontinuation include:

1. The subject is lost to follow-up.
2. The judgment of the principal investigator that the patient is too ill to continue.
3. Pregnancy
4. Voluntary withdrawal; a patient may remove himself/herself from the study at any time without prejudice. A patient may withdraw from the study at any time they wish to withdraw consent.
5. Significant and rapid progression of malignancy, requiring alternative medical, radiation or surgical intervention including, but not limited to, the development of CNS metastasis.
6. Grade 3 or 4 toxicity, which is unmanageable, unexpected, unrelated to chemotherapy, and attributable to protocol therapy, or a serious adverse event that requires the subject's being withdrawn from the trial.
7. Technical difficulties are encountered in the T cell genetic modification and expansion procedure that precludes the generation of clinical cell doses that meet all Quality Control criteria outlined in Section 15.3.
8. Termination of the study by the principal investigator, the sponsor, the study funder, the IRB, or the Food and Drug Administration.

##### **4.4.2 Data Collection and Follow-up**

Follow-up data collection after cell therapy clinical trials is specified by the FDA. As long as patients have detectable cells transduced with the lentiviral vector, they should be followed for toxicity, immune reactions, and any long-term adverse events. Many patients who respond to cell therapy may also have prolonged DFS but are also at risk for late relapse. Therefore,

CONFIDENTIAL

subjects will continue to be followed for 1) engraftment as long as patients are at risk (until evidence of loss of detectable transduced T cells), 2) DFS until there is disease progression or they begin a new cancer therapy (except for HSCT); 3) survival until the time of death; or until the patient withdraws consent for clinical data collection or until two years after the last subject's infusion.

In the event that a subject cannot return to the study site for follow-up visits because of subject preference or geographical concerns, the subject's primary care physician and/or local oncologist may be asked to provide information from the subject's medical record to the study team at protocol defined timepoints (including the results of any routine care examinations and/or laboratory assessments), and assist in the collection of protocol required blood samples which will be sent to the University of Pennsylvania for protocol required analysis. The local provider will be contacted by a member of the study team to assess any potential toxicity. In numerous previous cell therapy trials at the CHOP and UPENN, loss of follow-up is estimated to occur in less than 5% of cases. Every effort will be made to contact subjects who appear to be lost to follow-up in order to at least obtain survival data. In the event a subject fails to complete the follow-up requirements, documentation of all attempts to contact the subject includes at least 3 telephone contacts (on different days and at different times of the day), and a certified letter.

After subjects' complete or prematurely discontinue participation in this study, subjects will also be asked to participate in a separate 15 year long-term follow-up destination protocol to further evaluate long term adverse events related to the study product.

## **5 STUDY DRUG**

### **5.1 Description**

CART-19 cells are autologous T cells (collected from the patient) that have been engineered to express an extracellular single chain antibody (scFv) with specificity for CD19 linked to an intracellular signaling molecule comprised of a tandem signaling domain of the 4-1BB and TCR $\zeta$  signaling modules. The CART-19 cells are cryopreserved in infusible cryomedia and will be administered in either 1 or 2 bags. Each bag will contain an aliquot (volume dependent upon dose) of cryomedia containing the following infusible grade reagents: plasmalyte-A, dextrose, NaCl, up to 7.5% DMSO, dextran 40, human serum albumin with up to  $5 \times 10^9$  autologous T cells per bag.

Expected toxicities associated with infusion of CART-19 cells include transient fever, chills, nausea, and rigors. In order to minimize these events, patients will receive premedication as instructed below in section 5.4. Later toxicities (7-21 days post infusion) are likely to be related to cytokine release syndrome (CRS), or possibly tumor lysis. Toxicities that could potentially occur but are unprecedented are primarily related to the gene transfer and are described in Section 8.4.2. These include generation of a replication competent lentivirus (RCL), insertional oncogenesis, and uncontrolled proliferation of the CART-19 cells.

### **5.2 Patient Eligibility to Receive CART-19 Transduced T Cells**

- Disease response:

[figure not shown]
CONFIDENTIAL

- No evidence of high disease burden, that would, in the opinion of the treating physician, put the patient at significant potential risk for tumor lysis syndrome.
- Failure to maintain performance status as indicated in initial eligibility criteria
- If s/p allogeneic transplant, 6 months from transplant.
- Patients experiencing toxicities from their preceding cytoreductive chemotherapy will have their infusion schedule delayed until these toxicities have resolved. The specific toxicities warranting delay of T cell infusions include:
  - Pulmonary: Requirement for supplemental oxygen to keep saturation greater than 95% or presence of radiographic abnormalities on chest x-ray that are progressive
  - Cardiac: New cardiac arrhythmia not controlled with medical management
  - Hypotension requiring pressor support
  - Active Infection: Positive blood cultures for bacteria, fungus, or virus within 48 hours.

CNS3 cohort infusion criteria:

- 1) Disease status:
  - a. If CNS3 by spinal fluid involvement, stable/responding disease as indicated by:
    - i. stable or decreasing CSF WBC, and
    - ii. total CSF WBC < 100 in a sample obtained within 72 hours of CART-19 infusion.
  - b. If CNS3 by MRI findings, there must be interval stability or improvement on MRI within 2 weeks of infusion
  - c. If CNS3 by cranial nerve findings, there must be stability or improvement of these cranial nerve findings on exam post intervention
- 2) At least 21 days since any prior CNS3 patient was infused.
- 3) Patients with CNS3 disease requiring radiation therapy must be at least 8 weeks post radiation at CART-19 infusion
- 4) Patients must have no acute/ongoing neurologic toxicity > Grade 1 with the exception of a history of controlled seizures or fixed neurologic deficits that have been stable/improving over the past 3 months

**5.2.1 Release criteria for the manufactured T cell product:**

CONFIDENTIAL

### 5.3 Treatment Regimen

#### 5.3.1 Patients 1-72 (infused), including CNS3 cohort

CART-19 transduced T cells will be given, up to a total dose of  $1.5 \times 10^7$ - $5 \times 10^9$  ( $0.3 \times 10^6$ - $1.0 \times 10^8$ /kg)- total cells transduced with the 41BB-z vector. We will use the following schedule, starting with a 10x dose reduction but allowing for intra-patient dose escalation (see section 6.6):

- Day 0: 10% of total dose
- Day 1: 30% of total dose if patient is clinically stable from prior day's infusion

See section 6.6 for details on timing and doses of subsequent CART-19 infusions. The toxicities that would preclude the next dose of T cells are DLTs or GVHD attributable to the cell infusion, and not toxicities attributable to the prior chemotherapy, such as cytopenias. A DLT will prevent the infusion of the next dose, even if fully resolved by that time.

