## STUDY SUMMARY AND STUDY SCHEMA

[figure not shown]
Title	A PHASE I/IIA STUDY OF REDIRECTED AUTOLOGOUS T CELLS ENGINEERED TO CONTAIN ANTI-CD19 ATTACHED TO TCR ZETA AND 4-1BB SIGNALING DOMAINS IN PATIENTS WITH CHEMOTHERAPY RESISTANT OR REFRACTORY CD19+ LEUKEMIA AND LYMPHOMA
Short Title	CD19 redirected autologous T cells
Phase	Phase I/IIa
Methodology	Open-label approach
Study Duration	Approximately 4-5 years
Study Center(s)	CHOP [REDACTED]
Objectives	The primary objective is to determine the safety and survival of the redirected autologous T cells transduced with the anti-CD19 lentiviral vector (referred to as “CART-19” cells) given in the context of an adult and a pediatric protocol targeting CD19+ malignancies.
Number of Subjects	72 infused, up to 86 enrolled
Diagnosis and Main Inclusion Criteria	Inclusion criteria are designed to include pediatric patients aged 1-24 years with CD19+ B cell malignancies with no available curative treatment options (such as autologous or allogeneic stem cell transplantation) who have limited prognosis (several months to <2 year survival) with currently available therapies.
Study Product, Dose, Route, Regimen	CART-19 cells transduced with a lentiviral vector to express either anti-CD19 scFv:TCR $\zeta$ or anti-CD19 scFv TCR $\zeta$ :41BB, administered by i.v. injection using an intra-patient dose escalation approach: 10% on day 0, 30% on day 1, possibly followed by 60% on day 14 (or later) with a total dose goal of $\sim 1.5 \times 10^7 - 5 \times 10^9$ ( $\sim 0.3 \times 10^6 - 1.0 \times 10^8$ /kg) T cells.
Duration of administration	Approximately 10-15 minutes; drug is expected to persist at detectable levels in circulation for weeks to months.
Reference therapy	None. This protocol will be given to subjects with unmet medical needs for which there are no current curative therapeutic options.

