## 1.2 Investigational Agent

The investigational agent in this protocol is CART-19 cells [REDACTED]. Autologous T cells will be engineered to express an extracellular single chain antibody (scFv) with specificity for CD19. This will be expected to redirect specificity of the transduced T cells for cells that express CD19, a molecule that is restricted in expression on the surface of the malignant cells and on normal B cells. In addition to CD19 scFv, the cells will be transduced to express an intracellular signaling molecule comprised of either the TCR $\zeta$  chain or a tandem signaling domain comprised of 4-1BB and TCR $\zeta$  signaling modules. The scFv is derived from a mouse monoclonal antibody, and thus contains mouse sequences, and the signaling domains are entirely of the native human sequences. The CART-19 scFv plasmid was previously reported and was generously provided [REDACTED]. CART-19 T cells are manufactured by isolating the T cells by apheresis, and using lentiviral vector technology to introduce the scFv:TCR $\zeta$ :4-1BB into CD4 and CD8 T cells. In some patients, a control scFv:TCR $\zeta$ : will be introduced into a portion of the cells for the competitive repopulation experiment described below. These receptors are “universal” in that they bind antigen in an MHC-independent fashion, thus, one receptor construct can be used to treat a population of patients with CD19 antigen-positive tumors.

The CAR constructs were developed at the [REDACTED], and the clinical grade vector will be manufactured by [REDACTED] or another facility in accordance with the sponsor’s specifications, as outlined in the FDA-approved [REDACTED]. The CART-19 cells will be manufactured in the [REDACTED] according to the process shown in **figure 3**. At the end of cell cultures, the cells are cryopreserved in infusible cryomedia. The maximum total dose of CART-19 transduced T cells will consist of the infusion of  $1.5 \times 10^7$ - $5 \times 10^9$  ( $0.3 \times 10^6$ - $1.0 \times 10^8$ /kg) total cells. Each infusion will contain an aliquot (volume dependent upon dose) of cryomedia containing the following infusible grade reagents: plasmalyte-A, dextrose (5%), NaCl, up to 7.5% DMSO, dextran 40, human serum albumin with up to  $5 \times 10^9$  autologous T cells per bag. The initial dose will be decreased 10-fold, with intra-patient dose escalation (see Section 5.3 for details).

CONFIDENTIAL

CONFIDENTIAL

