Lentiviral vector clinical experience. Considerable data shows that retroviral vectors are safe when expressed in human T cells; however, retroviral vectors appear less safe when used in human stem cells. Lentiviral vectors have the potential to be safer from the perspective of insertional mutagenesis, and they have substantially higher efficiency for genetically engineering human T cells. Therefore, we propose to use lentiviral vector technology to introduce the CART-19 T body constructs into the T cells. [REDACTED]

[REDACTED]

[REDACTED]

[figure not shown]
[figure not shown]
[figure not shown]
CD19 immunotoxin experience. Ideally, the target antigens for T body/CIR anti-tumor protocols should be carefully chosen, so as to be expressed only by malignant cells and not by normal cells. CD19 expression has been reported to be restricted to the B cell lineage, and thus the expectation is that toxicity from CART-19 T cells should be confined to the hematopoietic compartment. Most importantly, CD19 is not expressed on hematopoietic stem cells. Empiric clinical data with CD19 antibodies, radiolabeled CD19 antibodies and anti-CD19 immunotoxins supports this contention, as the infusions have not caused aplasia. Furthermore, the widespread clinical use of anti-CD20 (Rituximab), targeting CD20, an antigen with a distribution of expression similar to CD19, has shown an acceptable clinical toxicity profile that would be expected from B cell depletion. Recent clinical trials using chimeric immune receptors targeting CD20 and CD19 have also shown that redirected T cell immunotherapy appears safe for these targets.

Pheresis experience in young children. We have extensive experience over the past 15 years pheresing young children for therapeutic cells on our high-risk neuroblastoma trials (median age 3 years; studies including CHP-594, CHP-667, CCG A3973, COG ANBL00P1 and ANBL0532, various NANT studies), as well as a protocol for multiple cycle stem cell transplant in young patients with medulloblastoma (COG 99703). The effective lower limit for pheresis is 6 kg, and the effective lower limit for Medcomp catheter placement (as opposed to a femoral line) is 12 kg. Young children will be evaluated for suitability as a pheresis subject using our standard apheresis SOPs as approved by FACT.

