### 1.7 Dose Rationale and Risk/Benefits

The primary objective of this protocol is to test the safety and feasibility of administering CART-19 cells to patients with advanced refractory hematologic malignancies. A secondary objective of this protocol is to determine which cytosolic signaling domain is superior for permitting CIR T cell engraftment and persistence. In this “competitive repopulation” scenario, we must administer a dose of cells that is 1) safe and 2) feasible to produce and can be tracked in the subject after infusion in order to determine if one T body construct is superior to the other. The basis for setting the starting dose was based on 1) Guidance for Industry: S6 Preclinical Safety Evaluation of Biotechnology-derived Pharmaceuticals; 2) Joint taskforce report from the BioIndustry Association (BIA) and the Association of the British Pharmaceutical Industry (ABPI) and 3) the available literature on phase I trials to date conducted with CIR T cells. The FDA guidance on safe starting dose (FDA Guidance for Industry: Estimating the Maximum Safe Starting Dose in Initial Clinical Trials for Therapeutics in Adult Healthy Volunteers) does not apply well for cell and gene therapy, and as such was not used to guide the selection of the starting dose for this study.

We believe that an initial i.v. dose of  $1.5 \times 10^7$ - $5 \times 10^9$  ( $0.3 \times 10^6$ - $1.0 \times 10^8$ /kg) CART-19 cells is optimal for this protocol. Because there are about  $1 \times 10^{12}$  T cells in a healthy adult (equivalent to  $2 \times 10^{10}$  T cells/kg), the proposed total (100%) dose is equivalent to about 0.5% of the total body mass of T cells. Therefore, we expect the initial frequency of cells to be present at about 0.5% at baseline following infusion. In addition, in our animal models, we find that a dose of 5 million cells per animal causes a robust antitumor response. The dose given to animals, when scaled, is similar to  $5 \times 10^9$  cells in humans. As an additional safety feature, the cells will be administered using an inpatient dose escalation approach (see section 6.6). The proposed dose in children is also consistent with or less than our prior T cell infusion trial in young children (CHP-667).

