    - Relapsed after prior autologous SCT.
  - e. B-cell prolymphocytic leukemia (PLL) with relapsed or residual disease after at least 1 prior therapy and not eligible for allogeneic SCT.
  - f. Diffuse large cell lymphoma or other high-grade NHL, previously identified as CD19+
    - Residual disease after primary therapy and not eligible for autologous SCT.
    - Relapsed after prior autologous SCT.
    - Beyond 1st CR with relapsed or persistent disease and not eligible or appropriate for conventional allogeneic or autologous SCT.
2. Age 1 to 24 years. Patients ages 22-24 will only be enrolled if they are currently being treated at CHOP or another pediatric facility/oncologist.

CONFIDENTIAL

3. Expected survival > 12 weeks
4. Creatinine < 2.5 mg/dl and less than 2.5x normal for age
5. ALT ≤ 5x normal
6. Bilirubin <2.0 mg/dl
7. Any relapse after prior SCT will make patient eligible regardless of other prior therapy.
8. Patients with relapsed disease after prior allogeneic SCT (myeloablative or non-myeloablative) will be eligible if they meet all other inclusion criteria and
  - a. Have no active GVHD and require no immunosuppression
  - b. Are more than 4 months from transplant (6 months at infusion; see Section 5.2)
9. For those patients who require leukapheresis for T cell collection (i.e. no previously collected product exists), adequate venous access for apheresis or eligible for appropriate catheter placement, and no other contraindications for leukapheresis.
10. Voluntary informed consent is given.
11. Patients with CNS3 disease will be eligible if CNS disease is responsive to therapy (at infusion, must meet criteria in Section 5.2) (see section 15.5 for definitions of CNS1, CNS2 and CNS3 disease)

NOTE on 1.a.vi – declines SCT: SCT is performed in patients with ALL in CR3, but the outcomes are problematic. Most data suggest about a 30% OS in the highly selected group of patients. A report which places this in context was published in JCO by Saarinen-Pihkala et al., looking at the overall (population-based) experience in CR3 ALL. Of 71 pts with ALL in CR3, OS after SCT was 30% and EFS 15%. Overall EFS of the 71 patients in CR3 was 7%. These numbers indicate that a decision to pursue a therapy other than SCT in CR3 ALL is rational, and that CART-19 therapy may offer a benefit to patients in this group.

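### The absolute and per-kilogram dose ranges coincide only at 50 kg, and the visible text does not say how they apply to patients of other weights

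*Combined protocol and SAP*

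**What the plan says.** Section 5.3.1, which covers infused patients 1 to 72 including the CNS3 cohort, reads "CART-19 transduced T cells will be given, up to a total dose of" 1.5×10^7 to 5×10^9 total cells and gives 0.3×10^6 to 1.0×10^8 per kg in brackets. Section 6.6 repeats this. Both sections set day 0 at 10% and day 1 at 30% of the total.

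The same two ranges stand side by side in four other places, under different labels:

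- Study Summary, after the 10% and 30% infusions: "possibly followed by 60% on day 14 (or later) with a total dose goal of" the range.
- Section 1.2: "The maximum total dose of CART-19 transduced T cells will consist of the infusion of" the range. The section adds that the first dose is reduced tenfold.
- Section 1.7: "We believe that an initial i.v. dose of" the range. The next sentence says that "the proposed total (100%) dose is equivalent to about 0.5% of the total body mass of T cells".
- Section 5.3.2, for the comparison cohort. That cohort is on hold pending redesign.

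On who may be dosed, section 4.1 gives "Age 1 to 24 years" and sets no weight criterion. Section 1.4, describing apheresis experience in young children, notes that "The effective lower limit for pheresis is 6 kg".

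**The concern.** Printing a per-kg range in brackets after an absolute range presents the two as the same quantity. That can be true at only one body weight. In a trial open from age 1 to age 24, many patients will be well away from any single weight, so the ceiling on the total dose has two values for the same patient. The 10%, 30% and possible 60% infusions are fractions of that total and inherit the ambiguity.

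The first stake is patient safety: two careful readers could take different maxima for the same small child. The second is interpretation. Sections 7.1 to 7.7 plan no summary of cells or cells/kg infused, so toxicity and week 4 engraftment would be reported without the exposure needed to read them.

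**Working it through.** **Inputs.** Absolute range 1.5×10^7 to 5×10^9 cells and per-kg range 0.3×10^6 to 1.0×10^8 (section 5.3.1 and the other places listed). Infusion fractions 10%, 30% and 60% (Study Summary; 5.3.1 and 6.6 for the first two). The 6 kg weight is the technical apheresis limit in section 1.4. The documents give no weight-for-age data, so 10, 20 and 70 kg are assumptions chosen to show the range.

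**Step 1: the weight at which the plan's two ranges agree.**

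- Lower limits: 1.5×10^7 / 0.3×10^6 = 50 kg.
- Upper limits: 5×10^9 / 1.0×10^8 = 50 kg.

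The bracketed figures therefore reproduce exactly with a 50 kg divisor. The same weight is implied elsewhere: section 1.7 equates 1×10^12 T cells with 2×10^10/kg (ratio 50), and section 6.4 pairs 50×10^9 white cells with 10^9/kg (ratio 50). The visible text never names 50 kg as a reference weight for dosing.

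**Step 2: other weights.** At weight W, the ratio of absolute to per-kg upper limit is 5×10^9 / (1.0×10^8 × W) = 50/W. The lower limits have the same ratio, 1.5×10^7 / (0.3×10^6 × W) = 50/W.

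| Weight (kg) | Per-kg range, in cells | Absolute / per-kg limit | Doses inside both ranges |
|---|---|---|---|
| 6 | 1.8×10^6 to 6.0×10^8 | 8.3 | 1.5×10^7 to 6.0×10^8 |
| 10 | 3.0×10^6 to 1.0×10^9 | 5.0 | 1.5×10^7 to 1.0×10^9 |
| 20 | 6.0×10^6 to 2.0×10^9 | 2.5 | 1.5×10^7 to 2.0×10^9 |
| 50 | 1.5×10^7 to 5.0×10^9 | 1.0 | 1.5×10^7 to 5.0×10^9 |
| 70 | 2.1×10^7 to 7.0×10^9 | 0.71 | 2.1×10^7 to 5.0×10^9 |

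Below 50 kg the per-kg upper limit is the smaller of the two; above 50 kg the order reverses.

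**Step 3: the fractions.** At 10 kg and the upper limit, the day 0 infusion is 0.10 × 5×10^9 = 5×10^8 cells on the absolute scale and 0.10 × 1.0×10^9 = 1×10^8 on the per-kg scale. Days 0 and 1 together are 0.40 × 5×10^9 = 2×10^9 against 0.40 × 1.0×10^9 = 4×10^8.

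**Step 4: does another limit settle it?** Section 5.4 caps infused volume at 10 cc/kg. At 6 kg that allows 60 ml. Section 5.7 allows up to 5×10^9 cells in a bag or syringe of 10 to 50 ml. The cap restricts volume, not cell number, and does not choose between the ranges.

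**Step 5: the label.** Section 1.7 applies *initial* to a range that its own next sentence, the Study Summary and sections 1.2, 5.3.1 and 6.6 treat as the total. With day 0 at 10% of the total, the two labels differ tenfold if read literally.

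**The case against.** The best reply has five parts.

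- **Missing text.** Section 5.3.1 refers to section 6.6 for dosing details, part of 6.6 was not available, and the release criteria in 5.2.1 are not shown. A rule of precedence could sit there. This stands: the claim is limited to the visible text.
- **No arithmetic error.** The brackets reproduce exactly at 50 kg, a weight that the protocol uses implicitly elsewhere, so they may be a restatement for a reference patient. This also stands. The defect is ambiguity, not miscalculation.
- **No forced contradiction.** A reader might infer that no dose can meet both ranges in a small child. The table shows otherwise: the ranges overlap at every weight listed and could be applied jointly. But the visible text does not say that they are, so the ceiling remains unclear.
- **The 6 kg figure.** A reader might infer that the trial plans to collect cells from 6 kg children. Section 1.4 gives only a technical limit, drawn from experience on other trials, with case-by-case evaluation. The 8.3 is an extreme, not an expected value.
- **The label.** A reader might infer a tenfold conflict in the operative dosing. The documents do not support that: *initial* is one slip in the rationale section, and 5.3.1 and 6.6 agree on 10% of the total at day 0.

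**Conclusion.** The point holds as an ambiguity in a stated dose limit. The two ranges agree at 50 kg and nowhere else. Away from that weight their limits differ by a factor of 50/W: 5.0 at 10 kg, 2.5 at 20 kg and 0.71 at 70 kg on assumed weights, and 8.3 at the technical apheresis limit of 6 kg. It should be corrected because the ambiguity concerns a maximum dose in children and is cheap to remove. The initial/total label is a minor matter of consistency.

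The conclusion rests on the visible text containing the whole rule, which cannot be confirmed. It does not show that any child would receive an excessive dose. Nor should a reader infer that a planned estimate or a power figure is damaged: the analysis in section 7.7 is primarily descriptive, and no sample size or power figure depends on dose.

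**What to change.** The sponsor should reconcile the dose statements in the Study Summary and in sections 1.2, 1.7, 5.3.1 and 6.6, and in 5.3.2 when that cohort is redesigned, so that the limits are unambiguous at every eligible weight. Any rule that the sponsor intends will serve this purpose, including joint application of the two ranges. If the unavailable part of 6.6 or the release criteria already contain the rule, a cross-reference from each statement is enough. The label in 1.7 should be made consistent with the other sections. This review takes no view on which limit is right.

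In section 7, add a per-patient table of cells and cells/kg actually infused, by infusion and in total, beside the safety and engraftment results.

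The cost is a wording amendment and one descriptive table. Weight is collected at baseline (section 6.2). The sponsor should confirm that the infused cell number is captured as a data item, since the statistical sections do not name it.
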